## Primary estimands of secondary Pharmacokinetic endpoints

### Steady State PK of GSK3036656

The clinical question of interest is:

What are the estimates (mean/ median and variability) of steady state PK parameters ( $AUC_{(0-\tau)}$ ,  $C_{max}$ ,  $C_\tau$  and  $T_{max}$ ) of GSK3036656 in the presence of EE/LNG in healthy female participants, who are missing no more than one 20 mg dose of GSK3036656 in treatment period 2 and are 100% compliant with study treatments in treatment period 3?

The Primary Estimand is described by the following attributes:

- Population: Healthy female participants of non-childbearing potential aged 18 to 65 years.
- Endpoints:  $AUC_{(0-\tau)}$ ,  $C_{max}$ ,  $C_\tau$  and  $T_{max}$  for GSK3036656
- Treatments: single dose Microgynon+14 days GSK3036656
- Strategy for intercurrent event: The intercurrent events of interest are participants missing their dose of Microgynon during treatment period 3, or missing a dose of GSK3036656 in treatment period 3, or missing more than one 20 mg dose of GSK3036656 in treatment period 2. The strategy for handling all of these intercurrent events will be a Principal Stratum Strategy, where we are only interested in the strata of participants who are missing no more than one 20 mg dose of GSK3036656 in treatment period 2 and are 100% compliant with study treatments in treatment period 3.
- Population-level summary:
  - For  $AUC_{(0-\tau)}$ ,  $C_{max}$ , and  $C_\tau$  of GSK3036656: Descriptive Statistics (including n, Arithmetic means with 95% CI, Geometric means with 95% CI, CV%, SD, Median with Min, Max);
  - for  $T_{max}$  of GSK3036656: Descriptive Statistics (including n, Median with Min, Max).

Rationale for estimand: Interest lies in estimating the pharmacokinetics of GSK3036656 in the presence of Microgynon, which cannot be accurately assessed in the situation where participants are missing more than one 20 mg dose of GSK3036656 in treatment period 2 and are not 100% compliant with study treatments in treatment period 3.

## Pharmacokinetics of EE/LNG

The clinical question of interest is:

What are the estimates (mean/ median and variability) of the PK parameters ( $AUC_{(0-t)}$ ,  $T_{max}$  and  $t_{1/2}$ ) of EE and LNG with and without GSK3036656 in healthy female participants, who, for the estimates with GSK3036656 are missing no more than one 20 mg dose of GSK3036656 in treatment period 2 and are 100% compliant with doses of GSK3036656 in treatment period 3? For the estimates of PK parameters of EE and LNG taken alone, no intercurrent events are defined.

The Primary Estimand is described by the following attributes:

- Population: Healthy female participants of non-childbearing potential aged 18 to 65 years.
- Endpoints:  $AUC_{(0-t)}$ ,  $T_{max}$ , and  $t_{1/2}$  for EE and LNG
- Treatments: single dose Microgynon+ 14 days GSK3036656 and single dose Microgynon

Strategy for intercurrent event: The intercurrent events of interest, applicable to estimates of PK parameters for EE and LNG with GSK3036656 only, is participants missing one or more doses of GSK3036656 in treatment period 3, or missing more than one 20 mg dose of GSK3036656 in treatment period 2. The strategy for handling this intercurrent events will be a Principal Stratum Strategy, where we are only interested in the strata of participants who are missing no more than one 20 mg GSK3036656 dose in treatment period 2 and are 100% compliant with doses of GSK3036656 in treatment period 3. For the estimates of PK parameters of EE and LNG taken alone, no intercurrent events are defined.

- Population-level summary:
  - For  $AUC_{(0-t)}$  and  $t_{1/2}$  (h) of EE and LNG: Descriptive Statistics (including n, Arithmetic means with 95% CI, Geometric means with 95% CI, CV%, SD, Median with Min, Max);
  - for  $T_{max}$  of EE and LNG: Descriptive Statistics (including n, Median with Min, Max).

Rationale for estimand: Interest lies in estimating the pharmacokinetics of Microgynon, with and without GSK3036656. The PK of Microgynon taken with GSK3036656 cannot be accurately assessed in the situation where participants are missing more than one 20 mg dose of GSK3036656 in treatment period 2 or are not compliant with doses of GSK3036656 in treatment period 3.

## Primary estimand of secondary Safety endpoints

### For all secondary safety endpoints the primary clinical question of interest:

[figure not shown]
Are GSK3036656 and Microgynon, taken separately or together, safe and well tolerated in healthy female participants of non-childbearing potential aged 18 to 65 years, regardless of study treatment discontinuation and the level of compliance of either treatment?

The primary estimands for Safety are described by the following attributes:

- Population: Healthy female participants of non-childbearing potential aged 18 to 65 years.
- Endpoints:
  - Incidence of serious adverse events within each treatment period.
  - Incidence of adverse events of grade 3 severity or higher within each treatment period.
  - Incidence of adverse events considered by the investigator to be possibly, probably or definitely related to study drug (overall and separately for Microgynon and GSK3036656) within each treatment period.
  - Incidence of participants withdrawn from the treatment/study due to adverse events within each treatment period.
  - Incidence of ECG values of PCI within each treatment period.
  - Incidence of clinical chemistry laboratory values of PCI within each treatment period.
  - Incidence of haematology laboratory values of PCI within each treatment period.
  - Incidence of vital signs parameters of SBP, DBP and HR of PCI within each treatment period.
- Treatments: single dose Microgynon, once daily GSK3036656 and single dose Microgynon +once daily GSK3036656
- Strategy for intercurrent event: The intercurrent events of interest are participants missing the dose of Microgynon, missing one or more doses of GSK3036656 or discontinuing GSK3036656 early due to any reason. The strategy for handling these intercurrent events will be a Treatment Policy Strategy, where all safety data after the intercurrent event will be included.
- Population-level summary: Frequency and percentage of participants; with the denominator for percentages being the number of participants entering the treatment period.

Rationale for estimand: It is important to document all safety issues that could potentially be attributable to the regimen, regardless of treatment non-compliance/discontinuation.

## 1.2. Study Design

Overview of Study Design and Key Features	
 
Participants progress immediately from the end of Treatment Period 1 to Treatment Period 2, with no washout required in between.
	
Design Features	
 
• A Phase 1, open-label, fixed-sequence, 1-way DDI study.
 
• Participants will be screened within 14 days before the start of Treatment Period 1. The treatment periods are then as follows: 
 
– Treatment Period 1: Microgynon only
 
– Treatment Period 2: GSK3036656 only
 
– Treatment Period 3: Microgynon + GSK3036656
 
 
 
• Approximately 20 participants will be enrolled to ensure at least 16 participants provide evaluable data in both test and reference periods.
 

Study intervention	
 
• Treatment Period 1: Microgynon (0.03 mg EE/0.15 mg LNG) single dose on Day 1 of the treatment period.
 
• Treatment Period 2: A loading dose of GSK3036656 40 mg on Day 4 then GSK3036656 20 mg od from Day 5 to Day 14.
 
• Treatment Period 3: Microgynon (0.03 mg EE/0.15 mg LNG) single dose co-administered with GSK3036656 20 mg on Day 15, then GSK3036656 20 mg od alone from Day 16 to Day 17.
 

Study intervention Assignment	
 
• This is an open-label study. All eligible participants will receive the same treatments.
 

Interim Analysis	
 
• No interim analysis is planned for this study.
 

## 2. STATISTICAL HYPOTHESES

The primary objective, as outlined in Section 1.1, is planned to be addressed using formal hypothesis testing. For the primary estimand, the following (confirmatory) two 1-sided hypothesis is planned to be tested for Microgynon+GSK3036656 (Treatment Period 3) versus Microgynon alone (Treatment Period 1):

$$H_0: \mu_{\text{test}} / \mu_{\text{ref}} < 0.8 \text{ or } \mu_{\text{test}} / \mu_{\text{ref}} > 1.25$$

$$H_a: 0.8 \leq \mu_{\text{test}} / \mu_{\text{ref}} \leq 1.25$$

Where  $\mu_{\text{test}}$  is the geometric least squares (LS) mean for PK parameters ( $AUC_{(0-\infty)}$  and  $C_{\max}$ ) of EE/LNG when coadministered with GSK3036656 and  $\mu_{\text{ref}}$  is the geometric LS mean for PK parameters of EE/LNG when administered alone. The hypothesis test will be assessed using Schuirmann's two 1-sided t-test procedure with  $\alpha=0.05$  for each test [D. J Shuirmann, 1987]. Each ratio will be compared to 0.8 and 1.25 as described above. Lack of effect (i.e. lack of a drug-drug interaction) will be demonstrated if the 90% confidence intervals (CIs) for both PK parameters ( $AUC_{(0-\infty)}$  and  $C_{\max}$ ) for both EE and LNG are within 0.8 and 1.25 (four parameters in total).

### 2.1. Multiplicity Adjustment

Not applicable. Although there are four comparisons, the null hypothesis must be rejected in all four cases, so no adjustment to the type 1 error is required.

## 3. ANALYSIS SETS

Analysis Set	Definition / Criteria	Analyses Evaluated
Screened	
 
• All participants who signed the ICF and were screened for eligibility.
 
• This population will be used for screen failure listing and summary.
 
	Study Population
Enrolled	
 
• All participants who entered the study (who received study intervention or underwent a post screening study procedure).
 
• Note screening failures (who never passed screening even if rescreened) and participants screened but never enrolled into the study (Met eligibility but not needed) are excluded from the Enrolled analysis set as they did not enter the study.
 
	Study Population
Safety	
 
• All participants who received at least 1 dose of study medication.
 
• Participants will be analyzed according to the actual study intervention.
 
	Safety

Analysis Set	Definition / Criteria	Analyses Evaluated
	
 
This population will be used for all demographic and safety summaries and listings.
 
	
PK	
 
All participants in the Safety analysis set who had at least 1 non-missing PK assessment (NQ values will be considered as non-missing values).
 
Data will be reported according to the actual study intervention.
 
This population will be used for PK summary tables, statistical analysis tables, figures, and listings.
 
	PK

## 4. STATISTICAL ANALYSES

### 4.1. General Considerations

Plasma EE, LNG, and GSK3036656 concentration-time data will be analyzed by the Clinical Pharmacology Modelling & Simulation department, Parexel, using noncompartmental methods with Phoenix WinNonlin Version 8.3 or higher.

Statistical analysis will be performed by Clinical Statistics, GSK.

#### 4.1.1. General Methodology

Participants who prematurely withdrew from study will not be replaced.

Confidence intervals will use 95% confidence levels unless otherwise specified.

Unless otherwise specified, endpoints defined in Section 1.1 will be summarized using descriptive statistics and graphically presented (where appropriate). In summary tables, results will be presented by treatment periods (Microgynon only, GSK3036656 only, and Microgynon + GSK3036656).

Unless otherwise specified, continuous data will be summarized using descriptive statistics: N, n, mean, standard deviation (std), median, minimum and maximum; for PK concentration data, No. Imputed, between-subject CV (%CVb) and 95% CIs, will also be reported along with above mentioned summary statistics; categorical variables will be summarized using n and percentage of participants in each category; for Tmax, only N, n, median, minimum, and maximum values will be presented; loge-transformed plasma concentration and PK parameters will be summarized using geometric mean, 95% CI, SD (logs) and the geometric %CVb based on geometric mean.

To assess primary endpoint, loge-transformed PK parameters will be statistically analyzed separately using Analysis of covariance (ANCOVA) Model to report point estimate for the ratio of the geometric means of treatment groups under comparison along with 90% CIs.

Further details of analysis, including the full list of data displays to be produced, will be provided in the Output & Programming Specification (OPS).

#### 4.1.2. Baseline Definition

For all endpoints the baseline value (derived for each period) will be the latest pre-dose assessment of respective period with a non-missing value, including those from unscheduled visits. If time is not collected, Day 1, Day 4 and Day 15 assessments are assumed to be taken prior to first dose of the respective period and will be used as baseline.

Unless otherwise stated, if baseline data is missing no derivation will be performed and baseline will be set to missing.

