## CONFIDENTIAL

220104  
Protocol Amendment 1 Final

Procedure	Screening	Treatment Period 1			Treatment Period 2		Treatment Period 3			Early Withdrawal	Unscheduled	Notes
	D -14 to -1	D 1	D 2	D 3	D 4	D 5-14	D 15	D 16-17	D 18			
Serial PK sampling: GSK3036656•							X	X				PK samples collected predose (GSK3036656) and after dosing at 0.5, 1, 1.5, 2, 3, 4, 6, 8, 12, 24 hours relative to Day 15 dosing in Treatment Period 3. The Day 15 24 h sample must be taken prior to GSK3036656 dosing on Day 16.  The predose sample to be taken within 30 minutes prior to dose administration.  Blood is drawn for PK analysis at 0.5-4 hours ±5 minutes after dosing.  Blood is drawn for PK analysis at 6-12 hours ±20 minutes after dosing.  Blood is drawn for PK analysis at 24 hours ±1 hours after dosing.
AE review•		←-----→										AEs collected from the start of study intervention until day 18 of Treatment Period 3.
SAE review•		←-----→										SAEs collected from the signing of the ICF until Day 18 of Treatment Period 3.
Concomitant medication review•		←-----→										

AE = adverse event; D = Day; ECG = electrocardiogram; EE = ethinyl estradiol; LNG = levonorgestrel; PK = pharmacokinetic; SAE = serious adverse event.

Assessments performed predose on Day 4 of Treatment Period 2 were considered baseline for GSK3036656 dosing.

- Is used to indicate a study procedure that requires databasing (either in eCRF, laboratory or other third-party vendor).
- Is used to indicate a study procedure that does not require databasing (in source only).
- Participants may be admitted the night before Day 1 and Day 14, but study procedures will commence on the morning of Day 1 and morning of Day 15.

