### 7.1.2. QTc Stopping criteria

- If a clinically significant finding is identified (including, but not limited to changes from baseline in QT interval corrected using Fridericia's formula [QTcF] after enrolment, the investigator or qualified designee will determine if the participant can continue the study intervention and if any change in participant management is needed. This review of the ECG printed at the time of collection must be documented. Any new clinically relevant finding should be reported as an AE.

A participant that meets either bulleted criterion below based on average QTc values of triplicate ECGs over a brief recording period (See Section 8.3.3) will discontinue study intervention and will be withdrawn from study intervention.

- QTcF  $> 500$  msec,
- Change from baseline in healthy participants: QTcF  $> 60$  msec

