#### **4.4.1. Additional Safety Assessments**

##### **4.4.1.1. Laboratory Data**

In addition to laboratory summaries related to PCI criteria, summaries of worst-case grade increase from baseline will be provided for all the lab tests that are gradable by CTCAE v4.03. These summaries will display the number and percentage of subjects with a maximum post-baseline grade increasing from their baseline grade. Any increase in grade from baseline will be summarized along with any increase to a maximum grade of 3 and any increase to a maximum grade of 4. Missing baseline grade will be assumed as grade 0. For laboratory tests that are graded for both low and high values, summaries will be done separately and labelled by direction, e.g., sodium will be summarized as hyponatremia and hypernatremia separately.

Change from period baseline values of haematology and chemistry will be summarized using descriptive statistics.

For lab tests that are not gradable by CTCAE v4.03, summaries of worst-case changes from baseline with respect to normal range will be generated. Decreases to low, changes to normal or no changes from baseline, and increases to high will be summarized for the worst-case post-baseline. If a subject has a decrease to low and an increase to high during the same time interval, then the subject is counted in both the “Decrease to Low” categories and the “Increase to High” categories.

Separate summary tables for haematology and chemistry laboratory tests will be produced. Liver function laboratory tests will be included with chemistry lab tests.

Protocol-required routine urinalysis tests will also be summarized descriptively.

An e-DISH plot of maximum post baseline total bilirubin versus maximum post baseline ALT will be created.

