##### **4.4.1.3. ECG**

ECG findings are defined from best to worst as: “normal”, “abnormal - not clinically significant”, and “abnormal - clinically significant”. The worst finding will be selected at each time point when there is repeat ECG. All ECG findings will be summarized by days.

The QTc data analysis will use the collected values based on Fridericia formula.

The QTc values based on Fridericia formula will be rounded to the integer and the values will be categorized into the following CTCAE grade and ranges: Grade 0 (<450 msec), Grade 1 (450-480 msec), Grade 2 (481-500 msec), and Grade 3 ( $\geq 501$  msec). Summaries of grade increase will be provided. These summaries will display the number and percentage of subjects with any grade increase, increase to grade 2 and increase to grade 3 for the worst-case post-baseline only. Missing baseline grade will be assumed as grade 0.

The changes in QTc values will be categorized into the clinical concern ranges which are specific to changes in QTc: 31-60 and  $>60$  msec. A summary of change in QTc value will display the number and percentage of subjects with a change within each range for the worst-case post-baseline only. Subjects with missing baseline values will be excluded from this summary.

A figure plotting the baseline QTc and the worst-case post-baseline values will be produced for each period. The figure will have reference lines at 450, 480 and 500 msec for both the x and y axes. There will be diagonal reference lines at equality (i.e. a 45-degree line), at equality plus 30 msec, and at equality plus 60 msec.

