## 6.2. Appendix 2 Data Derivations Rule

### 6.2.1. Change from Baseline

The change from baseline will be calculated by subtracting the period baseline values from the subsequent post-baseline values. If either the baseline or post-baseline value is missing, the change from baseline is set to missing as well.

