### 6.2.3.1. Laboratory Values

Haematology				
Laboratory Parameter	Units	Category	Clinical Concern Range	
			Low Flag (< x)	High Flag (>x)
Hematocrit	Ratio of 1	Male		0.54
		Female		0.54
		Change from Baseline	Decrease of 0.075	
Haemoglobin	g/L	Male	75	180
		Female	75	180
		Change from Baseline	Decrease of 25	
Lymphocytes	x10  / L		0.8	
Neutrophil Count	x10  / L		1.5	
Platelet Count	x10  / L		100	550
Red blood cell (RBC) count	million/mcL		4.2	6.1
Mean corpuscular volume (MCV)	fl.		80	100
Mean corpuscular hemoglobin (MCH)	picograms (pg)		27.5	33.2
%Reticulocytes	%		0.5	2
Monocytes	%		2	8
Eosinophils	%		1	4
Basophils	%		0.5	1
Clinical Chemistry				
Laboratory Parameter	Units	Category	Clinical Concern Range	
			Low Flag (< x)	High Flag (>x)
Calcium	mmol/L		2	2.75
Creatinine	%	Change from Baseline		Increase of 30%
Glucose	mmol/L		3	11
Potassium	mmol/L		3	5.5
Sodium	mmol/L		130	150
Direct bilirubin	mg/dl		<0.3	<0.3
Total protein	g/dl		6	8.3
Blood urea nitrogen (BUN)/Urea	mg/dl		5	20

Haematology				
Laboratory Parameter	Units	Category	Clinical Concern Range	
			Low Flag (< x)	High Flag (>x)
Creatine phosphokinase (CPK)	mcg/l		10	120
Homocysteine	µmol/L		4	14
Antiphospholipid antibodies	MPL		0	39.9
Sex hormone binding globulin (SHBG)	nmol/L		18	144

Liver Function				
Test Analyte	Units	Category	Clinical Concern Range	
ALT	IU/L	High	$\geq 3x$ ULN	
AST	IU/L	High	$\geq 3x$ ULN	
T Bilirubin	µmol/L	High	$\geq 1.5x$ ULN	

ULN = Upper Limit of Normal; ALT=Alanine Aminotransferase; AST=Aspartate Aminotransferase;

T. Bilirubin=Total Bilirubin

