### 6.2.4. Study Period

Assessments and events will be classified according to the time of occurrence relative to the study intervention period.

Treatment period 1 ranges from Day 1 dose to Day 4 predose, similarly treatment period 2 ranges from Day 4 dose to Day 15 predose and treatment period 3 ranges from Day 15 dose until Day 18.

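### The SAP splits the safety change over 14 continuous GSK3036656 dosing days at Day 15, so a change above a PCI threshold can go unflagged in both periods

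*SAP*

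**What the plan says.** - **Baseline.** SAP 4.1.2 states: "For all endpoints the baseline value (derived for each period) will be the latest pre-dose assessment of respective period with a non-missing value". SAP Table 2 applies this to ECG, chemistry, haematology and vital signs, with Day 1, Day 4 and Day 15 predose as the baselines of Periods 1, 2 and 3.
- **Change.** SAP 6.2.1: "The change from baseline will be calculated by subtracting the period baseline values from the subsequent post-baseline values". SAP 4.4.1.1 follows it for laboratory data: "Change from period baseline values of haematology and chemistry will be summarized using descriptive statistics". SAP 4.4.1.2 does the same for vital signs, and the QTc figure in SAP 4.4.1.3 is drawn for each period.
- **Period limits.** SAP 6.2.4: "treatment period 2 ranges from Day 4 dose to Day 15 predose and treatment period 3 ranges from Day 15 dose until Day 18".
- **Dosing.** Protocol 4.1 gives GSK3036656 on Days 4 to 14 in Period 2 and on Days 15 to 17 in Period 3, with no gap.
- **Reference point for the drug.** The footnote to the Schedule of Activities (Protocol 1.3, Table 1) reads: "Assessments performed predose on Day 4 of Treatment Period 2 were considered baseline for GSK3036656 dosing".
- **Change-based PCI flags.** SAP 6.2.3.1 and 6.2.3.2 define four: haemoglobin ("Decrease of 25", in g/L), a haematocrit fall of 0.075, a creatinine rise of 30%, and a QTcF rise above 60 msec. Haemoglobin also has an absolute low flag (<75 g/L) and QTcF an absolute flag (>450 msec). Haematocrit has no absolute low flag, and creatinine has no absolute flag.
- **QTcF stopping rule.** Protocol 7.1.2 uses a change criterion, "Change from baseline in healthy participants: QTcF" above 60 msec, without saying which baseline applies.

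**The concern.** For a drug given continuously over 14 days, the natural safety contrast is the pre-drug value against the value at the end of the course. Here that is Day 4 predose against Day 18. The SAP never forms it. It forms Day 4 to Day 15 and Day 15 to Day 18, and the second starts from a value already on drug.

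Two things follow. First, a participant whose total change exceeds a PCI threshold can stay below it in each part and be counted nowhere as a change-based event. Second, the change-based incidence shown for the combination period describes only the last three dosing days. An effect that has levelled off by Day 15 is caught in Period 2, but the combination period then shows no change-based finding.

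This matters most for haemoglobin and creatinine. A reduction in red blood cell count is the first GSK3036656 risk in the protocol's risk table (Protocol 2.3.1, Table 2), and the earlier clinical signal quoted there was itself a change from baseline to follow-up. The same table lists renal clearance of the drug as a concern.

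A missing value makes the gap wider. If Period 3 has no predose value, its baseline is missing under SAP 4.1.2 and the change is missing under SAP 6.2.1. If there is also no other on-drug Period 2 value, that participant contributes no GSK3036656 change at all, even with both Day 4 and Day 18 values on file.

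**Working it through.** **Dosing days.** Day 4 to Day 17 is 17 − 4 + 1 = 14 dosing days, matching the 14 days stated in the skin-depigmentation row of Protocol Table 2. Period 2 contains 14 − 4 + 1 = 11 doses and Period 3 contains 17 − 15 + 1 = 3. Day 15 predose thus follows 11 doses and Day 18 follows all 14.

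**Which changes escape.** Scheduled laboratory, ECG and vital-sign assessments around GSK3036656 dosing fall on Days 4, 15 and 18 only. Let T be the threshold, D the total change from Day 4 to Day 18, and f the share of D reached by Day 15 predose, with the change running in one direction. Period 2 sees f × D and Period 3 sees (1 − f) × D. Neither flag is raised while both stay within T, so the largest total that escapes is

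D = T / max(f, 1 − f).

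The documents do not give f, so a range is shown:

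| f (share reached by Day 15) | Haemoglobin, T = 25 g/L | Haematocrit, T = 0.075 | QTcF, T = 60 msec |
|---|---|---|---|
| 0.50 | 50.0 | 0.150 | 120 |
| 2/3 | 37.5 | 0.113 | 90 |
| 11/14 (linear over the doses) | 31.8 | 0.095 | 76.4 |
| 0.90 | 27.8 | 0.083 | 66.7 |
| 1 (plateau by Day 15) | 25 (nothing lost) | 0.075 (nothing lost) | 60 (nothing lost) |

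Creatinine is a percentage flag, so the two parts multiply. The extreme is 1.30 × 1.30 − 1 = 69%. Under linear build-up, 30% / (11/14) = 38.2%, and the Period 3 part is 1.382 / 1.30 − 1 = 6.3%, well below 30%.

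**Illustrations (assumed values).**

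- Haemoglobin of 130, 110 and 100 g/L on Days 4, 15 and 18 gives period changes of −20 and −10 and a total of −30. There is no change flag in either period, and 100 is above the absolute low flag of 75.
- QTcF rising by 45 and then 20 msec totals 65. It appears only in the 31–60 msec category in Period 2. With a Day 4 value of 385, Day 18 is 385 + 65 = 450, which is not above 450, so the absolute flag is missed too. From 386 it reaches 451 and is flagged.

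**What other planned outputs recover.**

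- *Mean change.* In participants with all three values, the mean Day 4 to Day 18 change is the sum of the two period means. The SD is not recoverable, because it needs the covariance between the two changes, and neither is participant-level incidence.
- *Grade-increase tables.* If the grade did not rise from Day 4 to Day 15, nor from Day 15 to Day 18, it cannot be higher on Day 18 than on Day 4. A net rise must therefore show in at least one period. These tables lose no event; they only split it by period.
- *QTc categories.* SAP 4.4.1.3 says: "The changes in QTc values will be categorized into the clinical concern ranges which are specific to changes in QTc: 31-60" and above 60 msec. A split rise can show in the lower category but not as a rise above 60.

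**The case against.** The best defence is that the SAP implements its own estimand. Both documents define the safety endpoints as incidence within each treatment period, and a baseline reset at each period start fits that definition. Nor does the footnote to the Schedule of Activities flatly contradict the SAP: Table 2 does use Day 4 predose for the GSK3036656-only period, and the footnote does not say that Day 18 must be compared with it. Both observations are fair, and the period analysis is not itself an error. But counting events within a period fixes where they are counted, not the reference value that defines a change. A Day 4-referenced flag on Period 3 values is still a within-period incidence.

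A second argument is that SAP 4.1.1 leaves the full list of displays to the Output & Programming Specification, which is not available here and might add the contrast. That possibility cannot be excluded. However, SAP section 1 says the SAP covers the full analyses, and a specification written from Table 2 would use the Day 15 baseline.

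Third, Protocol 4.3 expects exposure close to steady state by Day 8. For effects that track exposure, this puts f near 1, where little or nothing is lost. The f = 0.50 row would need the last three doses to do as much as the first eleven, so it is a bound and not an expectation. This argument limits the size. It does not settle when haemoglobin or creatinine levels off, since either may lag exposure.

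Finally, participant protection does not depend on these tables. Investigators review laboratory results and record clinically significant changes (Protocol 8.3.4), and the haematology stopping limits in Protocol 7.1.3 are absolute. That also stands; the gap is in reporting.

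**Conclusion.** The point holds. As written, the SAP has no participant-level measure of the change from before GSK3036656 to the end of its 14-day course, and four of its own change thresholds can be exceeded in total without a flag. Under linear build-up the missed totals are 25 to 31.8 g/L for haemoglobin, 0.075 to 0.095 for haematocrit, 30% to 38.2% for creatinine and 60 to 76.4 msec for QTcF. All these figures rest on an assumed f, a change in one direction, and no unscheduled values in between. Haematocrit and creatinine are the most exposed because no absolute PCI flag for a haematocrit fall or a creatinine rise stands behind the change flag.

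The practical weight is modest. The affected analysis is descriptive secondary safety in about 20 participants. The earlier study reported a mean haemoglobin change of −4.9 g/L against −1.5 g/L on placebo, with no PCI values, so few participants are likely to be affected. An expected number cannot be computed, because the documents give no within-participant SD. The primary PK conclusion is unaffected. The change is worth making because the missing contrast addresses a named risk and uses data already collected.

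**What to change.** Add to SAP 4.1.2, Table 2 and 6.2.1 a rule to this effect:

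> For Treatment Period 3, change from baseline and the change-based PCI flags (haemoglobin, haematocrit, creatinine, QTcF) will also be derived for Day 18 and any unscheduled Period 3 value against Day 4 predose.

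Keep the Day 15-referenced displays as the increment after Microgynon is added. State explicitly that Day 15 predose serves both as the last post-baseline value of Period 2 and as the baseline of Period 3. Day 4-referenced grade-increase tables are optional, since the existing ones lose no event.

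Separately, the QTcF change criterion in Protocol 7.1.2, the footnote to the Schedule of Activities and SAP Table 2 should be reconciled, so that the baseline for that criterion is named.

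The cost is one extra derived baseline and a few tables, with no new visits or samples. The one drawback is that effects already present before the Day 15 Microgynon dose will also appear in the new display. It must therefore be labelled as the cumulative GSK3036656 change and not read as an effect of the combination.
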